### 5.1.1 Additional Data Collection for DHS Linkage Study on COVID-19 Pandemic Impact Among UG3 Participants

We will use data collected by the Wisconsin Department of Health Services (DHS) to estimate the rates of COVID-19 infection, testing, hospitalization, and death, fatal and nonfatal drug overdoses, and vaccination against COVID-19, Hepatitis A and Hepatitis B in the UG3 cohort. To achieve our objectives, we propose a retrospective cohort study that will be facilitated by linking data from several DHS registries with UG3 participants. We propose to provide DHS colleagues with identifiable data from 991 of our prior research participants (identifiers: participant name, date of birth, gender, race, ethnicity, previous address, previous phone number, date of participation in our study) to facilitate linkage with several DHS registries. We are seeking approval for the DHS data linkage via a partial waiver of authorization, waiver of consent, and by maintaining a log of the protected health information provided to DHS per standardized disclosure logs (see here: <https://compliance.wisc.edu/wp-content/uploads/sites/102/2019/02/Accounting-for-Disclosures-Log-Research.pdf>). The linkage process is described below:

1. UW will provide a dataset containing a unique study identification number and participant name, date of birth, gender, race, ethnicity, previous address, previous phone number, and date of study participation to colleagues at DHS.

2. DHS will link identifiers with vital records data to identify the date (from study participation date through present day) and cause of any deaths that have occurred among participants of our prior study, from study participation date through present day.
3. DHS will link identifiers with COVID-19 data captured in WEDSS to identify the date of any COVID-19 tests, confirmed or probable infections, and hospitalizations.
4. DHS will link identifiers with WIR to identify the dates of all COVID-19 vaccination doses received and type of vaccine (brand or whether an mRNA/adenovirus vector vaccine).
5. DHS will link identifiers with WIR to identify the dates of all vaccine doses for hepatitis A or B received (including doses received before study participation, if possible).
6. DHS will link identifiers with hospitalization data to identify overdose events involving an emergency department visit or hospitalization.
7. DHS will remove and destroy identifiers and return the dataset(s) to UW containing the unique study identification number.
8. UW researchers will link the new dataset with variables collected in our prior cross-sectional survey using the unique study identification number, including sociodemographic (i.e., age, gender, race/ethnicity, housing, education, employment, income, marital status, health insurance coverage) and behavioral correlates (i.e., substances used and mode of use, mental health indicators and symptoms, addiction treatment history, personal and witnessed overdose history, awareness of how to respond to an overdose and access to naloxone, self-reported HIV and hepatitis C infection and treatment, where the participant primarily receives medical care, barriers to engaging in medical care, criminal justice involvement history, access to the internet and a cell phone, and self-stigma).

We will also be requesting that DHS provide an aggregate dataset with COVID-19 data to facilitate comparison of COVID-19 burden between the general population of Wisconsin and UG3 participants. Specifically, we will with monthly age-, sex-, racial/ethnic-, and county-stratified numbers of COVID-19 tests, vaccinations, confirmed or probable infections, hospitalizations, and deaths for Wisconsin (i.e., fully stratified by combined categories of these demographic variables within each county). For the vaccination outcome, we would like to have the number vaccinated with 2 doses of mRNA or 1 dose of Johnson&Johnson and the number with a 3rd mRNA dose or second shot of any type following 1 dose of a Johnson & Johnson vaccine. We hope to obtain the following categories of age (18-29, 30-39, 40-49, 50-59, 60-69, 70+), race/ethnicity (Non-Hispanic/Unknown ethnicity + white, Non-Hispanic/Unknown ethnicity + African American, Non-Hispanic/Unknown ethnicity + American Indian or Alaskan Native, Non-Hispanic/Unknown ethnicity + Other or Multiple races, Hispanic + any race), sex (male, female) within each county in Wisconsin by month, beginning March 1, 2020 to present. We will also request estimates of the monthly population size within each stratum.

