**Rapid testing for infectious diseases.** Upon enrollment, participants will provide 3 fingerstick whole blood samples for rapid testing of HIV, HCV and syphilis. Vivent Health prevention staff are trained to perform point-of-care tests for these infections using the Alere Determine™ HIV-1/2 Ag/AB Combo (Alere Inc., Waltham, MA); the OraQuick® HCV Rapid Antibody Test (OraSure Technologies, Bethlehem, PA); and the Syphilis Health Check™ (Trinity Biotech, Bray, Co Wicklow, Ireland), respectively. During the 20 minutes while awaiting test results, participants will complete an interviewer-administered survey (described below). If all 3 rapid tests are non-reactive, then the study visit will end after he or she has completed the questionnaire and received recruitment training and referral coupons. If any of the 3 rapid tests are reactive, then SSP staff will perform venipuncture to collect a blood specimen to be sent to the Wisconsin State Laboratory of Hygiene (WSLH) for confirmatory testing, record multiple methods of re-contacting the client, and arrange a follow-up visit to review confirmatory test results and provide linkage to care, if needed. In the event that a participant cannot provide a blood specimen for confirmatory testing due to poor venous access, they will be invited to return at a later date for another blood draw attempt. Those confirmed to have active HIV, HCV, or syphilis infection will be linked to a local provider with the assistance of a Vivent Health case manager.

**Laboratory-based confirmatory testing and specimen handling.** Specimens received by WSLH will be processed for confirmatory testing per standard protocols (see Facilities and Resources for details). After completing the required testing and reporting test results to the testing agency and the WI Surveillance System, WSLH staff will store plasma specimens in preparation for shipping to the CDC and/or GHOST laboratories, as described in Section 5.2

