### Data analysis for Aim 1 DHS Linkage Study on COVID-19 Pandemic Impact Among UG3 Participants.

To estimate the impact of the COVID-19 pandemic on UG3 participants, we will use merged UG3-DHS data to determine several rates and correlates of interest, which are described in detail below.

**COVID-19 outcomes.** To examine risk and protective factors for COVID-19 related outcomes among people who inject drugs, we will use a time-to-event analysis approach (i.e., Kaplan Meier curves and survival analysis with Cox Proportional Hazards regression models) to quantify COVID-19 testing, infection, vaccination, hospitalization, and mortality rates and predictors of these outcomes among participants of our prior study. This will involve excluding our prior study participants who were deceased prior to the start of the US COVID-19 pandemic (March 1, 2020) and calculating person-

time as the number of days from March 1, 2020 through the date of outcome data provided from DHS.

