*Overdose outcomes.* We will use a time-to-event analysis approach (i.e., Kaplan Meier curves and survival analysis with Cox Proportional Hazards regression models) to quantify fatal overdose rates (from vital records data) and nonfatal overdose rates (from hospitalization data) and predictors of these outcomes among people who inject drugs. This will involve calculating person-time as the number of days from study participation date through the date of outcome data provided from DHS. We will examine sociodemographic and behavioral risk and protective factors (covariate list provided in the appendix) by quantifying hazard ratios. We will also examine whether overdose rates changed pre- and post-COVID-19 by including a time covariate with an interaction term indicative of the period (before March 1, 2020 vs. on/after March 1, 2020). If there are a sufficient number of fatal and nonfatal overdose events per county of residence (>5 events), we will also create maps of overdose rates by county. We may also describe results by county by creating maps. Any rates or counts involving fewer than 5 individuals will be suppressed (i.e., the results will not be viewable on a map), consistent with confidentiality standards of DHS.

*Hepatitis vaccination outcomes.* We will describe vaccination prevalence and use a time-to-event analysis approach (i.e., Kaplan Meier curves and survival analysis with Cox Proportional Hazards regression models) to quantify predictors of hepatitis A and B vaccination among people who inject drugs. We will calculate vaccination prevalence overall (defined as being vaccinated on or before

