HIV DIAGNOSIS AND TREATMENT (HHIHIV SERIES)	Questions on whether participant has been tested for HIV, last HIV test date, test results, date of diagnosis, HIV treatment
HCV DIAGNOSIS AND TREATMENT (HHIHCV SERIES)	Questions on HCV diagnosis, treatment for HCV, and main place for medical care for HCV
BACTERIAL INFECTIONS	Hospitalization of serious bacterial infection, date of hospitalization
ACCESS TO MEDICAL CARE	Main place participant received medical care, barriers to care

KESSLER DISTRESS SCALE (KES SERIES)	Questions on participants anxiety and depressive symptoms in the last 30 days
PTSD SCALE	Questions on whether participant experienced adverse event, and symptoms experienced after adverse event
ACCESS TO PREVENTION AND TREATMENT (ACC SERIES)	Questions on accessibility to condoms, HIV treatment, HCV treatment, STI treatment, buprenorphine, naloxone, clean syringes, vaccinations, infection information
CRIMINAL JUSTICE	Times law enforcement has stopped and searched participant, number of arrests, probation in the last 6 months, days they were in jail
SEXUAL RISK (SXR SERIES)	Number of partners in the past 30 days, trade sex for drugs, last time they had vaginal or anal sex, sex without a condom, sex without a condom and injected drugs, sex with HIV+
DEMOGRAPHICS	Main source of income, services received, relationship status, student status, pregnancy status, forms of birth control, homelessness, transportation, health insurance
RDS	Questions on their network of people who inject drugs
RAPID RESULTS	Results from HIV, HCV, and Syphilis testing that was done that day
DUP_ID	Possible participants that entered the study more than once
Qualitative Participant Interviews	
All transcripts were stripped of the following information:	Names Geographic subdivisions smaller than a state All Dates Telephone numbers FAX numbers Email addresses Social security numbers Medical record numbers Health plan number Account number Certificate/license number License plate number Device identifiers/serial numbers Web urls Internet protocol addresses Biometric identifiers Full face photos and comparable images

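### The DHS linkage study names only self-reported HIV and hepatitis C infection as its infection covariate, although UG3 participants were to be tested at enrolment and the rapid results are held under the study ID.

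*Combined protocol and SAP*

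**What the plan says.** Section 5.1.1, step 8, describes the covariate side of the linkage: "UW researchers will link the new dataset with variables collected in our prior cross-sectional survey using the unique study identification number". It then names sociodemographic and behavioral correlates. Among the behavioral ones is "self-reported HIV and hepatitis C infection and treatment". No test result is named. Step 3 asks the state surveillance system for COVID-19 data only, so the linkage brings in no registry HIV or hepatitis C status either.

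Section 6.0 puts such correlates into Cox models. For COVID-19 it will quantify "mortality rates and predictors of these outcomes among participants of our prior study". For overdose, and in the same words for hepatitis A and B vaccination, "We will examine sociodemographic and behavioral risk and protective factors (covariate list provided in the appendix) by quantifying hazard ratios". Appendices 1 to 3 as supplied contain no such covariate list.

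Section 5.1 sets out testing in the same cohort: "Upon enrollment, participants will provide 3 fingerstick whole blood samples for rapid testing of HIV, HCV and syphilis". Reactive tests go to the state laboratory for confirmation. On the order of events: "During the 20 minutes while awaiting test results, participants will complete an interviewer-administered survey". Table 6 defines Aim 1 prevalence from point-of-care screening plus laboratory confirmation. Appendix 3 lists a rapid-results element in the UG3 data: "Results from HIV, HCV, and Syphilis testing that was done that day".

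**The concern.** The study holds a tested baseline value and names a poorer one for the models. A participant who did not know of an infection at enrolment enters as uninfected, and one who reports an infection that has since cleared may enter as infected. Some such participants are to be expected: section 1.3 notes syringe-program clients who had never been tested for hepatitis C.

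Two things are at stake. Where infection itself affects the outcome, the hazard ratio for hepatitis C may be pulled towards 1 and adjustment for infection is incomplete. Where knowledge of infection or contact with care affects the outcome, as it may for hepatitis vaccination or COVID-19 testing, a single self-report variable cannot tell the two effects apart. The plan gives no reason for preferring self-report and no misclassification or sensitivity analysis.

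**Working it through.** The plan states no event count, power or target hazard ratio for the linkage study, so there is no figure of its own to reproduce. The check has two parts.

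**1. What the visit sequence implies.** The survey is answered before the result is read (section 5.1). An infection unknown to the participant until that visit therefore cannot appear in self-report. Afterwards, "Those confirmed to have active HIV, HCV, or syphilis infection will be linked to a local provider". So self-report taken before the result also misstates awareness during follow-up for anyone newly found to be infected.

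**2. How much a misclassified exposure could matter.** All inputs here are assumptions, because the documents give no prevalence or accuracy figures for self-report. Let p be the prevalence of active hepatitis C, s and c the sensitivity and specificity of self-report, and h the true hazard ratio. Misclassification is taken as unrelated to the outcome.

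- Infected share of self-reported positives: PPV = ps / [ps + (1-p)(1-c)]
- Infected share of self-reported negatives: q = p(1-s) / [p(1-s) + (1-p)c]
- Observed ratio ≈ [PPV·h + 1 - PPV] / [q·h + 1 - q]

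Results for h = 2.0:

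- p = 0.45, s = 0.65, c = 0.85: PPV = 0.2925/0.375 = 0.780; q = 0.1575/0.625 = 0.252; ratio = 1.780/1.252 = 1.42. With c = 0.90 it is 1.48, and with c = 0.95 it is 1.55.
- Lowest over p 0.30-0.60, s 0.50-0.80, c 0.85-0.95 (p = 0.60, s = 0.50, c = 0.85): PPV = 0.30/0.36 = 0.833; q = 0.30/0.64 = 0.469; ratio = 1.833/1.469 = 1.25.
- Highest (p = 0.30, s = 0.80, c = 0.95): PPV = 0.24/0.275 = 0.873; q = 0.06/0.725 = 0.083; ratio = 1.873/1.083 = 1.73.
- Infected share of self-reported negatives over this range: 8% to 47%.

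With perfect specificity and s from 0.5 to 0.9, a true 2.0 appears as 1.40-1.92 and a true 1.5 as 1.24-1.47. As an illustration of power (Schoenfeld formula, two-sided 5%, an assumed 150 events, h = 1.5, p = 0.5, c = 1), correct classification gives 0.70. Self-report gives 0.27, 0.41 and 0.59 at s = 0.5, 0.7 and 0.9.

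**HIV.** With an assumed p = 0.02 and c = 1, a true 2.0 appears as 1.98-2.00 for s = 0.5-0.9, so missed infections hardly matter. This needs false-positive reports to be very rare. At s = 0.7 and c = 0.98, PPV = 0.014/0.0336 = 0.417, q = 0.006, and the ratio is 1.417/1.006 = 1.41. The documents do not suggest that such false reports occur.

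**If awareness drives the outcome.** Suppose infected people who know their status have a ratio of 2.0, those who do not know have 1.0, and c = 1. Self-report then gives 2.00, and tested status gives 2s + (1-s), which is 1.50, 1.70 and 1.90 at s = 0.5, 0.7 and 0.9. Here the test-based ratio is the smaller one.

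**The case against.** The strongest reply is that the covariate set is under-specified rather than wrong. Step 8 introduces its list with an open word. The items spelled out are sociodemographic and behavioral, and a laboratory result is neither. Other sections speak more broadly of linking UG3 data or the original cohort data, Appendix 3 places the rapid results among the survey elements, and the covariate appendix cited in section 6.0 may name them. This stands to the extent that test results are not excluded. It does not remove the point, because the only infection measure the plan actually names is self-report.

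A reader might infer that the hazard ratios for both infections are certainly diluted. The documents do not support that. Attenuation needs error unrelated to the outcome and a true ratio other than 1. For testing and vaccination outcomes, awareness may be the operative predictor, and the ratio can then go either way. For HIV, missed cases are immaterial if prevalence is low.

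A reader might also infer that self-report should simply be replaced by one variable already in hand. That goes too far as well. The hepatitis C rapid test detects antibody, so active infection needs the laboratory confirmation, which Appendix 3 does not list. Section 5.1 allows for participants who could not give a confirmatory sample, and self-report carries its own information on awareness.

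Finally, these are exploratory analyses with no stated infection hypothesis, and hepatitis C is one item in a long list. That limits the weight of the point.

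**Conclusion.** The point holds as a cheap improvement to the linkage analysis. It is established from the documents that self-report is the only infection covariate named, that testing at enrolment was planned, that rapid results are held under the study ID, and that hepatitis C infections first found at enrolment are coded as uninfected under self-report. It is not established that any reported hazard ratio will be biased by a known amount. For outcomes driven by infection itself, the hepatitis C ratio may be attenuated, from 2.0 to about 1.25-1.73 under the assumed prevalence, sensitivity and specificity. The direction is uncertain for testing and vaccination, and the effect for HIV is negligible at low prevalence if false-positive reports are very rare.

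**What to change.** In step 8, add the study's baseline test status as the infection covariate for the Cox models in section 6.0:

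- Hepatitis C: antibody negative; antibody positive and RNA negative; RNA positive; reactive but unconfirmed.
- HIV: confirmed positive or not.

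Keep self-report as a separate awareness variable, or cross-classify participants as aware positive, newly found positive, or negative. Use self-report for infection only where no test result exists, and flag those records. Supply the covariate list that section 6.0 cites, and report agreement between self-report and test.

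The cost is small. The merge is done by study ID at UW after DHS returns the data, with no new specimens or participant contact. It does need the state laboratory's confirmation results as well as the rapid result, and some confirmations will be missing. Baseline status may also have changed before COVID-19 follow-up starts on March 1, 2020: the UG3 phase is dated to August 2019, and confirmed cases were to be linked to care. That limitation applies equally to self-report and should be stated.

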## ***5.2. Global Hepatitis Outbreak Surveillance Technology (GHOST).***

This research study is part of a collaboration with scientists at other institutions including the U.S. Centers for Disease Control and Prevention (CDC) and the Global Hepatitis Outbreak and

Surveillance Technology (GHOST) Center located at the Ragon Institute of MGH, MIT and Harvard. Blood collected as part of the testing for HIV, Hepatitis and Syphilis may be sent to these other institutions for additional testing. These research tests include, but are not limited to, HIV, HCV, Syphilis and/or other tests for research purposes only. All blood and information will be coded with a number and no directly identifiable information will be shared outside of UW-Madison. The GHOST lab will use specialized technology that identifies transmission links between HCV infected research subjects. The GHOST platform is a secure cloud-based public health research tool to allow state and local health departments to act more quickly to detect and fight the spread of Hepatitis C. Specimens utilized for this laboratory-based initiative will be collected and shared in the context of two complementary protocols:

1. A baseline, retrospective evaluation of HCV transmission clusters using remnant serum specimens currently stored at the Wisconsin State Laboratory of Hygiene.
2. An analysis of prospectively collected blood specimens obtained from individuals who undergo rapid testing for HIV, HCV and syphilis as part of their participation in this study.

### **5.2.1. Retrospective analysis of HCV transmission clusters in Wisconsin.**

We have analyzed data reported to the Wisconsin Electronic Disease Surveillance System (WEDSS) to identify cases of HCV infection that were reported for the first time between January 2016 and December 2017. Approximately 15% of all HCV cases reported to the surveillance system during this time represented individuals who underwent fee-exempt confirmatory HCV RNA testing through WSLH; these instances typically reflect testing done in public health settings such as syringe exchange programs and correctional facilities, and not traditional health care settings. This results in a sample that is enriched for younger people with a history of injection drug use. By contrast, birth cohort testing in WI has been conducted mostly in primary care settings, which utilize commercial or hospital based laboratories for confirmatory testing.

We have identified 241 individuals residing in one of the targeted rural catchment areas who were confirmed to have an HCV RNA+ sample analyzed at WSLH during 2016-17. In addition, we have identified an additional cohort of 218 individuals who we consider likely to represent recent or acute infections because of younger age, higher HCV viral load, or having received a designation of acute HCV infection at the time of reporting to WEDSS. The rationale for including the latter group, who were identified regardless of their geographic area of residence, is that they may enhance the overall likelihood of detecting transmission clusters. Characterization of transmission clusters that include residents of rural and non-rural communities would be highly informative for development of services in the proposed UH3 phase of the study.

Pending approval by the funding agencies and the appropriate institutional review boards, we will identify residual serum specimens corresponding to these 459 cases and ship samples to the GHOST laboratory at MGH. Specimens will be labeled with a unique identifying code and year of collection prior to shipping. GHOST investigators will be sent a corresponding database that specifies the year of collection and quantitative HCV RNA result, but will not receive other information that could be used to identify study participants. After GHOST investigators perform genetic sequencing of

the virus to understand transmission networks, data will be uploaded to a secured web interface in order for researchers and the Department of Health Services to access, according to procedures described below (5.2.2.)

